### 6.2 Full Analysis Set (FAS)

Because the Intention-to-Treat (ITT) principle is so difficult to achieve in practice, the ICH-E9 guidelines allow for a Full Analysis Set, which “is used to describe the

analysis set which is as complete as possible and as close as possible to the intention-to-treat ideal of including all randomised subjects”.

For this study, the Full Analysis Set will include all randomized patients, but exclude patients who clearly did not have a cardiac cause for their cardiac arrest.

At the Blind Review Meeting held on 5Mar 2018 by the Steering Committee, it was decided to exclude 3 patients from the FAS because their cardiac arrest was due to asphyxia.

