6.9.3. General statistics

All data will be managed by the LCC in conjunction with the Steering Committee. Data will be entered and reviewed on an ongoing basis. Key listings and tables will be defined by the Steering Committee. Tables, listings and raw data (as SAS transport files) will be made available to the members of the Steering Committee upon request.

The statistical analysis of the primary and all secondary efficacy endpoints will be performed in the modified Full Analysis Set (FAS), defined as all randomly assigned patients except those withdrawing informed consent for use of all trial data and in case many protocol violations are observed throughout the study, a Per Protocol Set (PPS) will be defined and all efficacy analyses will be repeated on the PPS.

All continuous data will be presented by treatment group using the number of non-missing observations, mean, standard deviation, median and (Q1,Q3). Categorical data will be presented by treatment group using the observed frequencies and percentages for each category.

The primary endpoint (% voxels with ADC < 0.650 mm²/s) will be analyzed by means of an analysis of variance (ANOVA) that includes randomized group and initial shockable rhythm as factors. The treatment effect will be estimated by the difference between treatment groups and presented along with its corresponding 95% confidence interval. Missing values for patients who die prior to the DW-MRI will be imputed on the basis of age, gender, presence of basic life support, presence of initial shockable rhythm, duration of advanced life support, neuron specific enolase, presence of a malign EEG pattern on day 1, final outcome at ICU discharge and allocated treatment arm.

Continuous and normally distributed secondary endpoints will be analyzed by means of an ANOVA including randomized treatment and initial shockable rhythm as factors in the model. Estimated treatment differences will be presented with their 95% confidence interval. Continuous secondary endpoints that show serious deviations from a normal distribution will be analyzed by means of a Van Elteren that includes the initial shockable rhythm as stratification factor. Binary secondary endpoints will be analyzed by means of a stratified Chi-squared test. Treatment differences will be expressed as risk ratios and presented along with their corresponding 95% confidence intervals.

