## 1 Purpose

This document provides a detailed description of the statistical analyses prescribed in the final protocol (version 4, dated 20Jan2017), that will be performed for the evaluation of the primary safety, secondary efficacy, clinical and safety endpoints of the NEUROPROTECT study.

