### 4.2 Final Analysis and Reporting

Upon final database lock, statistical analyses of the data will be performed according to the methods described in this document.

Any deviations will be documented.

The analysis populations were finalised at a Blinded Review Meeting on 5Mar2018 that was held by the Steering Committee upon inclusion of all patients into the study. The decisions made at this meeting were documented in the Analysis Sets document.

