### **6.3 Per Protocol Set (PPS)**

Patients from the FAS with major protocol deviations will be excluded from the per-protocol set (PPS).

The Per Protocol Set was reviewed and finalized at the Blind Review Meeting which took place on 5Mar2018 by the Steering Committee.

All major protocol deviations that lead to exclusion from the PPS are fully documented in Analysis Sets Document.

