## 10 Primary and Secondary Endpoints

### 10.1 Primary Endpoint

The primary endpoint will be summarised by randomised treatment group.

Since it is expected that a substantial proportion will have missing data for the primary endpoint (due to early mortality or other reasons), a statistical analysis that does not take account of this missingness is very likely to be subject to considerable bias.

Therefore, missing primary endpoint data will be imputed using the imputation model described in section 7.4.

In each imputation sample, the data will be analysed using an ANOVA that includes a factor for randomised treatment and the stratification factor of shockable rhythm. The results of the analyses will then be combined with standard methodology, using SAS PROC MIANALYZE.

The effect of randomised group will be estimated by the difference between groups and presented along with its associated 95% confidence interval.

The statistical analysis of the primary endpoint will be performed for the FAS and PPS.

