### 10.2 Secondary Endpoints

The statistical analysis of all secondary endpoints will be performed for the FAS and PPS.

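### The SAP's Full Analysis Set drops randomised patients whom the protocol keeps, and no planned efficacy analysis puts them back

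*SAP*

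**What the plan says.** Protocol section 6.9.3 assigns the primary and all secondary efficacy endpoints to a modified FAS of "all randomly assigned patients except those withdrawing informed consent for use of all trial data". If many violations occur, a per-protocol set (PPS) is added and the efficacy analyses are repeated on it.

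SAP section 1 presents the document as a description of the analyses prescribed in protocol version 4. SAP section 6.2 nevertheless says that "the Full Analysis Set will include all randomized patients, but exclude patients who clearly did not have a cardiac cause for their cardiac arrest". It then reports that at the blind review meeting "it was decided to exclude 3 patients from the FAS because their cardiac arrest was due to asphyxia". On timing, SAP section 4.2 says: "The analysis populations were finalised at a Blinded Review Meeting on 5Mar2018", once all patients had been included.

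SAP section 6.3 forms the PPS by removing patients from the FAS. Section 10.1 says "The statistical analysis of the primary endpoint will be performed for the FAS and PPS", and section 10.2 says "The statistical analysis of all secondary endpoints will be performed for the FAS and PPS". The subgroup analyses (section 7.8) use the FAS, and the Safety Set (section 6.1) serves safety data only.

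**The concern.** The SAP adds an exclusion that the protocol does not contain, does not identify it as a change, and gives no rule for deciding when a non-cardiac cause is clear. It also leaves out the protocol's consent-withdrawal exclusion, so the two definitions differ in both directions.

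The three patients were not necessarily ineligible. Protocol section 6.3.1 requires only a presumed cardiac cause, and section 6.4 lists hypoxic arrest among the causes to be recorded. If they were violations, the protocol's own route for violations is the PPS.

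At stake is whether the primary result rests on the randomised population that the protocol prescribes. Treating staff knew the assignment (protocol section 6.1), and neither document says who classified the cause of arrest or when. An exclusion settled after enrolment on a judgement of this kind can, in principle, remove patients unequally between arms. As planned, no analysis would show whether the conclusion holds with everyone included.

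**Working it through.** **1. Which set each SAP efficacy analysis uses**

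| Analysis | Set | Are the 3 patients in it? |
|---|---|---|
| Primary endpoint (10.1) | FAS, PPS | No |
| Secondary endpoints (10.2) | FAS, PPS | No |
| Subgroups (7.8) | FAS | No |

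The PPS is a subset of the FAS and cannot restore them. The SAP's sensitivity analyses (10.2.2, 10.2.11) deal with missing CPC and tracheostomy data, not with the population. So no SAP efficacy analysis covers the protocol's set.

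**2. The plan's sample size, used as a yardstick**

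Inputs (protocol 6.9.1, SAP 5): 56 per arm, SD 8.9 points, 80% power, two-sided alpha 0.05, 40% relative reduction. The control mean is not given, so 56 cannot be reproduced independently. Assumed control means of 10%, 12% and 15% give 78, 54 and 35 per arm. Solving backwards from 56:

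- Target difference = 8.9 × (1.960 + 0.842) × √(2/56) = 4.71 points (4.75 with the t distribution).
- Implied control mean = 4.71 / 0.40 = 11.8%.

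**3. Loss of numbers**

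Assumption: exactly 112 were randomised, 56 per arm.

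- Share removed: 3/112 = 2.7%, leaving 109.
- Power at 4.71 points = Φ(4.71 / (8.9 × √(1/n₁ + 1/n₂)) − 1.960). This is 80.0% for 56/56, and 78.9% for either 55/54 or 56/53.

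Power is not the issue.

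**4. Possible shift in the primary difference**

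Assumption: all three lie *k* SD from the mean of the rest of their arm, in the same direction. Shares are of 4.75 points.

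| Split of the 3 | Formula | k = 1 | k = 2 | k = 3 |
|---|---|---|---|---|
| All in one arm | 3 × k × 8.9 / 56 | 0.48 (10%) | 0.95 (20%) | 1.43 (30%) |
| 2:1, net | 1 × k × 8.9 / 56 | 0.16 (3%) | 0.32 (7%) | 0.48 (10%) |

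With typical values (*k* near 0) the shift is near zero. Under simple 1:1 allocation the chance that all three fall in one arm is 2 × 0.5³ = 25% (24.3% with arms of exactly 56), and a 2:1 split has the other 75%.

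**5. Possible shift in CPC 3–5**

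Assumption: all three had a poor outcome, and the poor-outcome rate in the remaining patients is 60%, taken from the 40% good outcome in protocol section 4.1.

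- All in one arm: 3 × (1 − 0.60) / 56 = 2.1 points in that arm (2.7 at a rate of 50%, 1.6 at 70%).
- 2:1 split: net 1 × 0.40 / 56 = 0.7 points between arms.

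**The case against.** The best defence is that this is a disclosed, blinded and very small exclusion. SAP section 6.2 invokes the ICH E9 full-analysis-set concept, names its criterion, and gives asphyxia as the reason for the three exclusions. The criterion follows the first inclusion criterion, and the documents do not say what was presumed at entry, so the patients may have failed it. Cause of arrest precedes randomisation and is listed as a baseline item (protocol 6.4, SAP 9), so treatment cannot change it. SAP section 4.2 refers to an Analysis Sets document, not available for this review, which may hold the rule applied and the change record that protocol section 6.10 requires.

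Much of this stands. Blinding and the baseline nature of the variable lower the risk of selection, and what remains is unequal ascertainment by unblinded staff, of which there is no evidence. The upper figures are extreme. With an implied control mean of 11.8%, deviations of 2–3 SD (17.8–26.7 points) below such a mean are impossible. Any of the three without an MRI would be imputed under SAP section 7.4 from a model that omits cause of arrest. The 25% probability is only illustrative, because randomisation was stratified.

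None of it answers the main point. A reason for excluding three patients is not a reason for departing from the protocol's population. The ICH E9 wording that the SAP cites asks for a set as near as possible to all those randomised, and the SAP states no obstacle to including these three. Nothing in the documents shows that the rule was fixed before the cases were known. A record held elsewhere would not supply the missing analysis.

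**Conclusion.** The concern holds. The SAP's FAS contradicts the protocol's definition, and no planned SAP efficacy analysis uses the protocol's population. The likely numerical effect is small: about one point of power, and a shift in the primary difference between near zero and 10% of the target unless all three patients were in one arm with values well away from the rest, when it could reach 10–30%. These figures assume 112 randomised in equal arms, an SD of 8.9 and the back-solved target difference. The actual number randomised and the arms and outcomes of the three patients are not stated, so bias is possible but not demonstrated. The point should be fixed because it concerns the population for the primary result and is cheap to put right.

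**What to change.** - In SAP section 6.2, restore the protocol's FAS for the primary and secondary analyses: everyone randomised, less any who withdrew consent for use of all their data, with the three patients included.
- Move the exclusion of non-cardiac arrests to a labelled sensitivity analysis or to the PPS.
- In SAP section 8.1, which now lists reasons for exclusion only for the PPS, report any FAS exclusions and these three patients by arm with the reason.

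If the narrower set were kept as the main one, the minimum would be to record the change as protocol section 6.10 requires and add an all-randomised analysis of the efficacy endpoints. That would show whether the exclusion matters, but the headline result would still rest on a population the protocol does not prescribe.

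The cost is one paragraph of SAP text, one line in the disposition table, and a further run of the efficacy programs on the second set, including the 100 imputations and the bootstrap intervals. No recruitment is needed, because the three patients are already randomised.

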### **6.3 Per Protocol Set (PPS)**

Patients from the FAS with major protocol deviations will be excluded from the per-protocol set (PPS).

The Per Protocol Set was reviewed and finalized at the Blind Review Meeting which took place on 5Mar2018 by the Steering Committee.

All major protocol deviations that lead to exclusion from the PPS are fully documented in Analysis Sets Document.

## **7 General Issues for Statistical Analysis**

### **7.1 Analysis Software**

All analyses will be performed using SAS software version 9.41 or higher for Windows 8 or higher1.

### **7.2 Summary Statistics**

Continuous variables will be summarized by the number of non-missing data points, mean, standard deviation, median and interquartile range.

Categorical and ordinal variables will be summarized by treatment group by observed frequencies and percentages relative to the total number of non-missing items.

All summary statistics will be presented by treatment group and overall.

| Data collected at several time points during the trial will be presented by planned visit, regardless of when the visit actually took place.

### **7.3 Statistical Comparisons between Groups**

Since randomization was stratified by the presence of shockable rhythm, all comparisons between groups should account for this stratification.

So, an ANOVA using factors for randomized group and shockable rhythm will be used rather than a two-sample t-test for the comparison of continuous and normally distributed variables. Continuous variables showing serious deviations from normality will be compared using a Van Elteren test. This test will also be used for the comparison of ordinal data.

For binary and categorical data, a Cochran-Mantel-Haenszel test will be used.

For primary and secondary variables, the effect of treatment will be estimated by an appropriate statistic and presented together with its associated 95% confidence interval.

#### **7.4 Methods for Withdrawals, Missing Data and Outliers**

For the primary endpoint, multiple imputation methodology will be used to account for missing data. A total of 100 imputations will be done. The imputation model will include the following:

Age, gender, presence of bystander CPR, presence of initial shockable rhythm, neuron specific enolase at days 1-2-3-4-5, presence of a malign EEG pattern on Day 1 and allocated treatment and death within 7 days of randomisation.

#### **7.5 Data Transformations**

Since the main analyses are performed using general estimating equation (GEE) models, no transformation of the data will be necessary since these models are quite robust in the presence of deviations from the normality assumption.

For the analysis of the primary endpoint, data transformation using logtransformation can be considered if the model assumptions of normality and constant variance for the residuals are not met.

#### **7.6 Multicentre Study**

Although randomization was stratified by study site, the primary and secondary analyses will not take the stratification by study site into account.

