1. SYNOPSIS

Classification: Academic, Investigator Initiated Trial

Protocol Version and Date: Version 4, 20 Jan 2017

Title of Study: Neuroprotective goal directed hemodynamic optimization in post-cardiac arrest patients: a randomized controlled trial (the NEUROPROTECT post-CA trial)

Participating country: Belgium

Study Centers: 2 (UZ Leuven and ZOL Genk)

Study Period: 3 years

Anticipated start: July 2015

Anticipated completion: May 2018

Objectives:

The **primary objective** of the trial is to assess whether or not a new goal directed hemodynamic optimization strategy can reduce cerebral ischemia in post-cardiac arrest (CA) patients as quantified by diffusion weighted MRI (DW-MRI) to be performed at day 4-5 with quantification of the percentage of ischemic voxels with an apparent diffusion coefficient (ADC) below 0.650 mm²/s.

Secondary efficacy outcomes:

- Cerebral performance category 3-5 at discharge from the ICU CPC 1: return to normal cerebral function and normal living
CPC 2: Disability but sufficient function for independent activities of daily life
CPC 3: severe disability CPC 4: Coma
CPC 5: Death
- Cerebral performance category 3-5 at 180 days post-CA (assessed by trial investigators that are unaware of the treatment assignment)
- SF36 questionnaire at 180 days post-CA (assessed by trial investigators that are unaware of the treatment assignment)
- Neurocognitive testing at discharge from the hospital
- Biomarkers: Neuron specific enolase (day 1-2-3-4-5)

- Functional testing: Activities Daily Life (ADL) and 6 minute walking distance (6MWD) at discharge from the hospital
- Renal function: creatinine day 1-2-3-4-5 and urinary output day 1-2- 3-4-5.
- Length of stay in the ICU
- Duration of mechanical ventilation
- Placement of tracheostomy

Safety outcomes:

- Incidence of life threatening arrhythmias during intervention period
- Incidence of new onset atrial fibrillation during intervention period
- Incidence of pulmonary congestion requiring diuretics during intervention period

Methodology: Prospective, multi-centre, interventional open label investigator driven randomized controlled trial. Randomisation will be stratified by the presence of an initial shockable rhythm.

Number of subjects planned: A total of 112 pts are planned for this study.

Anticipated duration of trial: 3 years from first patient entered to last patient randomized

Diagnosis and main criteria for inclusion and exclusion:

Inclusion criteria:

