6. INVESTIGATIONAL PLAN

6.1. Study Plan and Design

Multicenter randomized controlled open label trial conducted in 2 tertiary care hospitals in Belgium (UZ Leuven, and ZOL-Genk). Eligible patients will be randomly assigned in a 1:1 ratio to goal directed hemodynamic optimization or standard care strategy. Randomization will be performed centrally at the Leuven Coordinating Centre for Clinical Trials with the use of a computer-generated assignment sequence and an interactive voice response system. Patients will be stratified according to the presence of an initial shockable rhythm. Health care professionals caring for the trial patients will be aware of the intervention assignments because of the inherent problems with blinding of MAP. Physicians performing neurologic prognostication, radiologist interpreting MRI's, study personnel assessing final outcomes and statisticians will be unaware of the intervention assignments. Unblinding of all data and the final analysis of all primary and secondary outcome parameters will be performed after inclusion of all study patients. Written informed consent will be obtained from a next of kin. If a next of kin or another designated person is not available, a procedure for inclusion in the study in emergency situations will be applied. A definitive post hoc consent form will ultimately be obtained from patients who survived but had been initially treated on the basis of the emergency consent. The ethical committees in the participating hospitals will approve the study protocol prior to enrolment of the first patient.

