#### 3.3 Method of Treatment Assignment and Randomisation

Randomization was performed by site and was stratified according to the presence of shockable rhythm.

Randomization was available daily for 24 hours via a centralized telephone Interactive Voice Response System (IVRS) at the LCC.

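### SAP 7.6 says randomisation was stratified by site, then leaves site out of the primary analysis without a reason, while the protocol names shockable rhythm only

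*SAP*

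**What the plan says.** On how patients were randomised:

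- Protocol synopsis: "Randomisation will be stratified by the presence of an initial shockable rhythm". Sections 6.1 and 6.5.2 say the same: "Patients will be stratified according to the presence of an initial shockable rhythm". None of the three mentions site.
- SAP 3.3: "Randomization was performed by site and was stratified according to the presence of shockable rhythm".
- SAP 7.6: "Although randomization was stratified by study site, the primary and secondary analyses will not take the stratification by study site into account". No reason follows.

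On how the data will be analysed:

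- SAP 7.3: "Since randomization was stratified by the presence of shockable rhythm, all comparisons between groups should account for this stratification". On that ground it replaces the two-sample t-test with an ANOVA. It names rhythm only.
- SAP 10.1 specifies "an ANOVA that includes a factor for randomised treatment and the stratification factor of shockable rhythm" in each imputed data set. Protocol 6.9.3 has the same two factors.
- The imputation list in SAP 7.4 begins "Age, gender, presence of bystander CPR, presence of initial shockable rhythm, neuron specific enolase at days 1-2-3-4-5" and goes on to EEG pattern, allocated treatment and early death. Site is not in it.
- Site appears only in SAP 7.8, as an exploratory subgroup with an interaction test.

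**The concern.** There are two problems, and the first does not depend on any numbers. The SAP describes site as part of the randomisation and the protocol does not, so the documents leave the actual allocation scheme unsettled.

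The second is the analysis. Stratifying by a prognostic factor balances it between arms, so the treatment estimate varies less from trial to trial. A model without that factor leaves the between-site variation in the residual, and the reported standard error does not reflect the gain. The confidence interval is then too wide and the test too strict. The reasoning SAP 7.3 gives for rhythm applies equally to site if 7.6 is accurate. The site subgroup in 7.8 does not help, because it changes neither the main estimate nor its standard error.

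At stake is some precision in a trial of 112 patients, where SAP 10.1 says "it is expected that a substantial proportion will have missing data for the primary endpoint".

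**Working it through.** **Inputs from the documents.** 56 patients per arm, SD 8.9 points, 80% power, two-sided alpha 0.05 (SAP 5); two sites (protocol 3.1); ANOVA with treatment and rhythm (SAP 10.1).

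**The plan's own figure.** The control mean is not given, so the 40% reduction cannot be turned into points and 56 per arm cannot be reproduced from stated inputs. Working backwards, SE = 8.9 × √(2/56) = 1.682. With 112 − 3 = 109 residual df, 80% power needs a difference of 4.754 points (noncentral t), which implies a control mean of 4.754/0.40 = 11.9%. That is feasible, and the sample size is not disputed here.

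**Cost of a site term.** Residual df go from 109 to 108 and the critical t from 1.9820 to 1.9822. If site explains nothing, power goes from 80.00% to 79.99%.

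**Cost of leaving site out, if randomisation was stratified by it.** Let R² be the share of outcome variance explained by site (assumed; not in the documents). With equal sites, the site difference on the total-SD reading is 2 × 8.9 × √R². The reported SE is too large by the factor 1/√(1−R²), so the effective critical value is 1.982/√(1−R²). The planning SD comes from a pilot at one university, so it could be read as a total SD or as a within-site SD. Both are shown (complete data, n = 112).

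| Assumed R² | 0 | 0.02 | 0.05 | 0.10 |
|---|---|---|---|---|
| Site difference, points (8.9 = total SD) | 0 | 2.5 | 4.0 | 5.6 |
| SE too large by | 0% | 1.0% | 2.6% | 5.4% |
| True alpha without site | 0.050 | 0.048 | 0.044 | 0.039 |
| Power without / with site, 8.9 = total SD | 80.0 / 80.0 | 80.2 / 80.8 | 80.6 / 82.0 | 81.2 / 84.0 |
| CI half-width without / with, 8.9 = total SD | 3.33 / 3.33 | 3.33 / 3.30 | 3.33 / 3.25 | 3.33 / 3.16 |
| Power without / with site, 8.9 = within-site SD | 80.0 / 80.0 | 79.4 / 80.0 | 78.5 / 80.0 | 76.9 / 80.0 |

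**Simulation, complete data** (blocks of 4 within site × rhythm, 60% shockable; 40,000 null and 20,000 alternative runs). With equal sites and R² 0.05 and 0.10, type I error without site is 0.0445 and 0.0396, and with site 0.0501 and 0.0507; power is 80.7 v 82.1% and 81.3 v 84.2%. A 20/80 site split gives a similar loss (1.3 and 2.9 points), as does a rhythm effect of R² 0.10 (1.4 points at site R² 0.05). A separate simulation with 65% shockable and a 6-point site difference gave type I error of 3.5% without site and 4.6% with it, and power of 80.9% and 84.2%.

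**If randomisation was by rhythm only** (20/80 split, R² 0 and 0.05), the ANOVA with site keeps its level (0.052 and 0.051). Power changes by −0.4 and +1.6 points.

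**Multiple imputation** (about 30% missing, assumed; 20 imputations rather than the planned 100; one covariate in place of the SAP 7.4 list; 4,000 alternative runs). With site in both models or in neither, the power forgone at R² 0.05 and 0.10 is 2.7 and 4.3 points with equal sites, and 2.1 and 4.1 points with a 20/80 split. Type I error with site is 0.044 to 0.051, and mean bias is at most 0.05 points. A smaller paired run gave 1.1 and 3.7 points (Monte Carlo SE about 0.6).

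The GEE, survivor-average, Cochran-Mantel-Haenszel and Van Elteren analyses, and a log-transformed outcome, were not simulated.

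**The case against.** The strongest reply is that this is a disclosed choice with no validity problem. SAP 7.6 says openly that site will be ignored, the primary model matches the protocol, and site is a prespecified subgroup factor. The error is conservative and arises only if site was a factor and is prognostic. An R² of 0.10 needs the two hospitals to differ by 5.6 points, more than the back-solved treatment effect of 4.75, although eligibility and background care are common to both. Power below 80% also needs 8.9 to be a within-site SD. The protocol never says rhythm is the only factor, and the wording in SAP 7.3 refers to rhythm. Changing a protocol-specified model after all patients were included, in an open-label trial, for an unknown gain, might be thought worse than adding site as a sensitivity analysis.

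Much of this stands as a limit on size. The site effect is unknown, the below-80% case is only one reading, and the imputation figures are noisy: at R² 0, power without site was 64.9% in one setting and 67.2% in another. In those runs the assumed missing data cost far more power than site does. SAP 7.3 and 7.6 do not contradict each other in their literal wording.

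None of it supplies the missing reason or settles the allocation scheme, and none of it shows a material cost of including site. The lateness is met by documenting the change before unblinding and keeping the protocol model as a sensitivity analysis.

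**Conclusion.** The concern holds, as something that should be fixed rather than a flaw that threatens validity. The documents do not agree on the stratification factors, and the SAP leaves out a factor it says was used without saying why.

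The statistical effect is a loss of precision, conditional on site having been a factor and being prognostic. On complete data with assumed R² of 0.02 to 0.10, it amounts to a standard error 1.0 to 5.4% too large and about 0.5 to 2.7 points of power on the total-SD reading. On the within-site reading, power is 79.4 to 76.9% instead of 80.0%. The assumed imputation setting gives 2.1 to 4.3 points at R² 0.05 to 0.10, and 1.1 to 3.7 in the smaller check. If either condition fails, the planned standard error is valid. Confidence is medium, because the documents give no site effect, site split or missing-data rate.

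**What to change.** 1. State in SAP 3.3 and 7.6, consistently with protocol 6.1 and 6.5.2, which factors the randomisation system used.
2. Replace SAP 7.6 so that site (two levels) enters the primary ANOVA and the SAP 7.4 imputation model, and enters the GEE models as one main effect.
3. Keep the rhythm-only ANOVA of protocol 6.9.3 as a sensitivity analysis.
4. Treat site × rhythm stratification of the Cochran-Mantel-Haenszel and Van Elteren tests as optional, depending on actual stratum sizes. With an assumed 60% shockable and a 20/80 site split, the smallest stratum has 112 × 0.20 × 0.40 ≈ 9 patients across both arms.
5. Note that SAP 10.2.3 takes its survival-model covariates from 7.4. Site would therefore enter the survivor-average weights, but the outcome comparison would not be adjusted for site. The SAP should say so.
6. Leave Gray's test and the site subgroup in 7.8 as planned.
7. If the team prefers to leave site out, give the reason in 7.6.

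The cost is SAP wording and one term in each model. Because protocol 6.9.3 fixes the ANOVA factors, the change must be recorded under protocol 6.10, including what data were available when it was made. All patients were already included at the blinded review of 5 March 2018 (SAP 4.2), so the change has to be made before the unblinding that follows database lock (SAP 3.4).
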